7. If a participant becomes pregnant during the study period, they will be withdrawn to eliminate any potential risk to the fetus, even though the mouthwash is low-risk.

Sampling method

This study will employ consecutive sampling with simple randomization of all eligible adult patients who present to the Oral and Maxillofacial Surgery (OMFS) clinic at Hospital Pakar USM and are scheduled for surgical removal of impacted mandibular third molars under local anesthesia during the study period (1st April 2025 to 31st January 2026).

Patients meeting the inclusion and exclusion criteria (outlined in Section 3.5) will be invited to participate. Those who provide informed consent will be enrolled, with recruitment proceeding consecutively until the target sample size is achieved ($n = 58$, accounting for a 10% anticipated dropout rate).

Enrolled participants will be randomized into one of two groups (intervention or control) using a simple randomization method based on a pre-generated random number list (see Section 3.13). This process ensures each participant has an equal chance of allocation to either group, minimizing selection bias.

Sample Size Determination

Objective 1: G*Power software version 3.1.9.7 will be used to calculate the minimum required sample size for determining the Landry wound healing index score of the ORAL7® Mouthwash group compared to the 0.2% chlorhexidine gluconate mouthwash group following the surgical removal of mandibular third molars. The sample size estimation will be conducted using an independent sample t-test with the following parameters: two-tailed analysis, an effect size of 0.8, a significance level (α) of 0.05, a power ($1-\beta$) of 0.8, and an allocation ratio of 1. Based on a standardized effect size of 0.8 as defined by Cunningham (1978), the total required sample size is 52, with 26 participants allocated to each group.

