Objective 2: G*Power software version 3.1.9.7 will be used to calculate the minimum required sample size to determine the pain scores of the ORAL7® Mouthwash group with the 0.2% chlorhexidine gluconate mouthwash group following surgical removal of mandibular third molars. The calculation will employ ANOVA for repeated measures with parameters including an effect size of 0.4 (as stated by Cunningham, 1978), a level of significance (α) of 0.05, a power ($1-\beta$) of 0.8, two groups, seven measurements, and a correlation of 0.5 among repeated measures. Based on these parameters, the total sample size required is calculated to be 32 participants.

Objective 3: G*Power software version 3.1.9.7 will be used to calculate the minimum required sample size to compare the mouth opening of the ORAL7® Mouthwash group with the 0.2% chlorhexidine gluconate mouthwash group following surgical removal of impacted mandibular third molars. The sample size will be estimated using an independent sample T-test with a two-tailed design, an effect size of 0.8 (as per Cunningham, 1978), a significance level (α) of 0.05, a power ($1-\beta$) of 0.8, and an allocation ratio of 1. Based on these parameters, the total sample size required is 52 patients, with 26 participants in each group.

The total sample size calculated based on all 3 objectives will be 52 patients. By anticipating 10% non-compliance and drop out of patients during this study, a final sample size of 58 patients will be included in this study and they will be randomized into 2 groups (interventional and control), with 29 patients in each group.

Research Tools and Variables

Research Tools

- a. Oral 7 mouthwash
- b. 0.2% chlorhexidine gluconate mouthwash
- c. SPSS software
- d. Landry wound healing index
- e. Visual analogue scale
- f. Metal ruler

Research Variables

- a. Demographic characteristic such as age, gender
- b. Angulation of impacted teeth
- c. Duration of surgery

Data collection method

This study is going to be conducted in the Oral and Maxillofacial surgery clinic of Hospital Pakar USM. Patients who require surgical removal of impacted mandibular third molar are enrolled and selected based on inclusion and exclusion criteria. Written informed consent to participate in the study will be taken from the subject without obligation. Informed consent can be withdrawn anytime by the subject throughout the study without penalty and continuation of care and treatment will not be affected.

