Data collection form will be prepared for each patient, to record:

- a. Subject identification number (ID)
- b. Age
- c. Gender

[figure not shown]
- d. Tooth angulation
- e. Duration of surgery
- f. Pain score (day 1 to 7)
- g. Numbers of analgesic consumed (day 1 to 7)
- h. Landry wound healing score on day 7

Randomization process- Following confirmation of eligibility and acquisition of informed consent, participants will be assigned a unique subject identification number and subsequently randomized into one of two study arms: the intervention group (ORAL7® Mouthwash) or the control group (0.2% chlorhexidine gluconate mouthwash). Randomization will be conducted using a computer-generated list of random numbers (generated via random.org) to ensure equal probability of assignment and to minimize selection bias. Allocation concealment will be maintained by preparing 58 sealed, opaque envelopes, each containing a number corresponding to one of the two groups. Participants will be asked to draw one envelope prior to surgery, which will determine their group assignment. The designated mouthwash, pre-packaged and unlabeled by a designated study assistant, will then be provided post-operatively.

Data Analysis

Data will be entered and analyzed using SPSS version 29.0.2.0. Descriptive statistics will be used to summarize the socio-demographic characteristics of subjects. Numerical data will be presented as mean (SD) or median (IQR) based on their normality distribution. Categorical data will be presented as frequency (percentage). G*Power software version 3.1.9.7 will be used for repeated measures ANOVA and independent t-test will then be used to determine the P-value. P-value 0.05 as non-significant.

Study flowchart

Sample recruitment

Patients planned for surgical removal of impacted mandibular third molars under local anesthesia will be selected based on inclusion and exclusion criteria. Only those agree to participate in this study will be recruited and written informed consent will be obtained from participants.

Randomization

All participants recruited in the study will be randomly assigned into 2 groups. One group will receive ORAL7® Mouthwash as postoperative mouth rinse and the other group is control, in which 0.2 % chlorhexidine gluconate mouthwash will be given. Randomization of participants will be conducted using random numbers generator (random.org).

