Total 2 rounds of examination are completed. Pairs of repeated scores are used to assess intra examiner reproducibility. Results will be analyzed using SPSS, intraclass correlation coefficient will be obtained and classified. Values less than 0.5 are indicative of poor reliability, values between 0.5 and 0.75 indicate moderate reliability, values between 0.75 and 0.9 indicate good reliability, and values greater than 0.90 indicate excellent reliability (Koo & Li, 2016). Assessment session will end when good or excellent reliability is obtained.

Clinical Procedures

Orthopantomogram (OPG) will be taken for routine pre-operative assessment. Cone beam computed tomography (CBCT) will be ordered if indicated. Written consent will be taken from patients. Mouth opening of the patients will be measured by using a metal ruler in millimeters from mesioincisal edge of upper right central incisor to mesioincisal edge of lower right central

incisor prior to surgery. Different relevant reference points can be taken if central incisor(s) is missing, and alternative points will be recorded in data collection form.

Patients will be disinfected and draped under standard procedure. All the surgeries will be performed by qualified operators under aseptic techniques. Local anesthesia will be achieved by administering inferior alveolar, long buccal, and lingual nerve blocks using 2 cartridges 2.2 ml of 2% Scandonest special (2% mepivacaine in 1:100,000 adrenaline).

Copious irrigation of the surgical site will be done using normal saline solution (40 ml) before the incision is made using no. 15 blade. A full mucoperiosteal envelope flap will be reflected. Buccal and distal bone guttering and the impacted mandibular third molar will be sectioned, when necessary, using surgical drill and normal saline irrigation, the tooth will be removed completely. Socket curettage and smoothing of sharp bony edges will be undertaken, flap and the extraction socket will be thoroughly irrigated with normal saline. Closure of the surgical wound will be done using 4-0 Vicryl suture. The duration of the surgery will be calculated from the time of incision till the last suture is given.

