Pain will be measured by using visual analogue scale from 0 to 10. Mouth opening will be measured by metal ruler using the same reference points as preoperatively. Soft tissue healing of the surgical site will be investigated using the Landry Healing Index of Landry, Turnbull and Howley. This index is intended to assess healing of extraction sockets one week after intervention based on the following parameters: tissue color, bleeding response to palpation, presence of granulation tissue, characteristics of the incision margins and the presence of suppuration. Each wound can be scored from 1 (very poor healing) to 5 (excellent healing) (Marini et al., 2019).

The total duration of involvement of each patient will be 8 days starting from the day of the surgery till the 7th post-operative day that is the day for follow-up visit. The duration of the first visit that is the day on which the surgery will take place will depend entirely on factors like type and position of impaction, surgeon's experience, tooth morphology and root anatomy, patient factors like mouth opening, anxiety level, cooperation etc. and will usually take around 45 minutes for completion. The duration of the follow-up visit will be around 30 minutes. This is the standard time for each patient. In case of breakthrough pain which cannot be controlled by celecoxib and paracetamol, the patient will be instructed to contact one of the investigators as soon as possible as per the contact information given in the patient consent form which will be given to each patient participating.

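### Angulation and duration of surgery are recorded but have no pre-specified role in the group comparisons: a possible efficiency and pre-specification gain, not an error

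*Combined protocol and SAP*

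**What the plan says.** Under Research Variables the plan lists demographic characteristics, "Angulation of impacted teeth" and duration of surgery. Both surgical variables appear again as items on the data collection form prepared for each patient. Clinical Procedures defines the second one: "The duration of the surgery will be calculated from the time of incision till the last suture is given".

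Data Analysis gives neither variable a role. Its descriptive sentence covers socio-demographic characteristics only. For the group comparisons it names repeated-measures ANOVA and says that an "independent t-test will then be used to determine the P-value". No covariate, regression or stratified analysis is mentioned.

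Randomisation is simple, with no stratification. On timing, the Randomization process paragraph says "Participants will be asked to draw one envelope prior to surgery", and the flowchart text likewise has the draw before the operation. The mouthwash is handed over after surgery and first used on post-operative day 1. The assessor, the principal investigator and the patient are described as blinded; the documents do not say whether the operators are.

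**The concern.** The trial is planned on 52 evaluable patients with almost no margin over 80% power for Objectives 1 and 3. If angulation or duration of surgery predicts healing or mouth opening, an adjusted comparison would be more precise with no extra patients. Pre-operative mouth opening is also measured, and it too has no stated role in the analysis of Objective 3.

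There is a second reason to settle this in advance. With about 26 patients per arm and no stratification, the arms may differ somewhat in these variables. If they do and the plan is silent, any adjustment would be chosen after seeing the data, and a reader could not tell whether it had been intended.

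**Working it through.** **Inputs from the documents.** Objectives 1 and 3: "two-tailed analysis, an effect size of 0.8, a significance level (α) of 0.05", power 0.80, equal allocation; for Objective 1, "the total required sample size is 52, with 26 participants allocated to each group", and Objective 3 gives the same numbers. Objective 2: effect size f = 0.4, "two groups, seven measurements, and a correlation of 0.5 among repeated measures", stated N = 32. Dropout 10%, final N = 58.

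**Assumptions, because the documents give no figure.** The share of outcome variance explained by the covariates (R²), taken as 0, 0.10, 0.20 and 0.30. The covariate degrees of freedom p: 1 for angulation in two levels; 2 for angulation in three levels, or in two levels plus one continuous covariate; 4 for angulation in four levels plus duration.

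**Step 1: the plan's own figures.**
- t-test: noncentrality = 0.8 × √(26/2) = 2.884 on 50 df, critical value 2.009, power 80.7%. The 26 per arm is reproduced.
- Repeated-measures ANOVA, between-group effect: λ = N f² m / (1 + (m − 1)ρ) = 32 × 0.16 × 7 / (1 + 6 × 0.5) = 8.96 on 1 and 30 df, power 82.5%. The 32 is reproduced.
- Dropout: 52 / 0.90 = 57.8, rounded up to 58.

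**Step 2: Objectives 1 and 3 with adjustment.** The variance of the adjusted difference, relative to the unadjusted one, is (1 − R²) × (N − 3)/(N − p − 3). With N = 52 this is (1 − R²) × 49/(49 − p). The noncentrality becomes 2.884 divided by the square root of that factor, on 50 − p df. Example with p = 2 and R² = 0.20: factor 0.80 × 49/47 = 0.834, noncentrality 2.884/0.913 = 3.158, power 87.2%.

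| Assumed R² | p = 1 | p = 2 | p = 4 |
|---|---|---|---|
| 0 | 79.9% | 79.0% | 77.2% |
| 0.10 | 83.9% | 83.1% | 81.4% |
| 0.20 | 87.9% | 87.2% | 85.7% |
| 0.30 | 91.7% | 91.1% | 89.9% |

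All are to be compared with 80.7% unadjusted. On variance, break-even is R² = p/49: about 2%, 4% and 8%. At R² = 0.20, the total N for 80% power falls from 52 to 44 (p = 2) or 46 (p = 4).

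**Step 3: pain at N = 52.** λ = 52 × 0.16 × 7 / 4 = 14.56, power about 96%. With p = 2 it becomes 95.6% at R² = 0 and 98.4% at R² = 0.20.

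**Step 4: chance imbalance.** The mean difference in a standardised covariate has SD √(2/26) = 0.277, so it exceeds 0.3 SD in about 28% of trials. At R² = 0.10, a 0.3 SD imbalance moves the estimate by 0.3 × √0.10 ≈ 0.09 SD, against a design effect of 0.8 SD.

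**The case against.** The strongest reply is that nothing is wrong. A randomised comparison needs no covariates, and the stated sample size is built on the unadjusted tests. The documents offer no evidence that either variable predicts an outcome. Excluding deep distoangular teeth also narrows the range of angulation. All of this stands, which is why the point is one of efficiency and pre-specification.

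A reader might infer more than the documents support, in four ways.

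- *That precision is definitely being given up.* Its size, and even its sign, depends on an R² that the documents do not state.
- *That chance imbalance is likely and biases the result.* It is neither. The 28% is for one covariate, and the t-test's error rate and interval already allow for such imbalance.
- *That the plan itself ties both variables to outcome.* The statement near the end of Clinical Procedures, "will depend entirely on factors like type and position of impaction", concerns the length of the first visit. Its list also includes surgeon's experience, anxiety and cooperation. It mentions neither angulation nor any outcome.
- *That duration of surgery is a baseline covariate like angulation.* The rinse cannot affect it, because rinsing starts on day 1. But it is recorded after the draw, and operator blinding is not stated. An operator who knew the allocation could, in principle, work differently.

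The cost of adjusting should not be played down either: with four angulation levels plus duration, about 3.5 points of power are lost if neither variable is prognostic.

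**Conclusion.** The point holds as a modest, low-cost improvement. Both variables are collected on every patient and no planned comparison uses them; the unadjusted analysis remains valid.

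For Objectives 1 and 3, with p from 2 to 4 and R² from 0 to 0.30, power moves from 80.7% to between about 77% and 91%. The variables must jointly explain more than about 4% (p = 2) or 8% (p = 4) of outcome variance to help. For pain there is little to gain. The figures assume a normal outcome and linear adjustment. The Landry score runs from 1 to 5, so they are approximate there. The case for pre-specification does not depend on R².

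**What to change.** In Data Analysis, before unblinding:

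1. Pre-specify angulation, collapsed in advance to two or three levels, as a covariate in all three comparisons.
2. Add pre-operative mouth opening as a covariate for Objective 3.
3. For Landry, state the adjusted model, linear or ordinal.
4. Report the unadjusted results alongside.
5. Use duration of surgery only in a sensitivity analysis, unless operators are documented as unaware of allocation.

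For patients not yet enrolled, draw the envelope after the last suture. Allocation then cannot influence the operation, and duration becomes a pre-randomisation value. The mouthwash is handed over only after surgery, so supply is unaffected. The flowchart text uses the drawn number as the subject ID; the ID would have to be issued separately, as the Randomization process paragraph already describes.

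Cost: a few lines of text, standard SPSS procedures and no new data. The risk is about 1 to 3.5 points of power if the covariates are not prognostic, towards the lower end if angulation is kept to two or three levels. Moving the draw is a small procedural change part-way through the stated study period: the document is dated 16 October 2025, about six and a half months into a period of 1 April 2025 to 31 January 2026. It cannot be applied to patients already treated, so the date of the change should be recorded.

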A list of random numbers will be generated for each group (total 58 numbers for 2 groups). Each group will have a set of 29 numbers. A container containing 58 papers with one written number on each will be prepared. Each participant will be instructed to draw a paper from the container before the surgical procedure commences. The number written in the paper will indicate the allocated group for the participant and as subject identification number.

Allocation concealment

The Dental Surgery Assistant (DSA) will identify the participants as control or interventional group, and mouthwash without label will be given to participants after completion of surgery.

Calibration

Intra and inter examiner calibration of Landry healing index will be conducted before study commences. It will consist of 2 sessions: alignment followed by assessment session. In this study, 2 examiners will be involved for assessment of Landry healing index score of surgical wounds after removal of impacted mandibular third molar.

Sample size for the calibration process will be calculated based on intraclass correlation, with 5 observations per subject, level of significance: 0.05, power: 0.8, minimum acceptable reliability: 0.6, expected reliability: 0.8, drop out 10% (Walter et al., 1998).

The sample size will be 28 for this study.

Calibration process will be repeated until full agreement is achieved between 2 examiners.

1) Alignment session

In this session, the Landry healing index will be explained. The clinical photographs of surgical site 1-week post-op with their respective Landry healing index scores are shown and explained. Agreement between 1st and 2nd examiner on the scoring will be obtained.

2) Assessment session

This session will begin after the alignment session. Subjects for assessment exercise will be recruited with entry criteria comparable to study subjects. Informed consent is obtained. Examiners will rotate among subjects to assess the surgical site of each subject and respective Landry healing index score is recorded.

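### The calibration sample size of 28 assumes five scores per subject, but each reliability estimate will have two, so power for the planning test is about 51–56% and not 80%; the two stopping rules also need reconciling

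*Combined protocol and SAP*

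**What the plan says.** All of this is in the Combined protocol and SAP, under Calibration and its Assessment session.

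- **Sample size inputs.** The exercise is sized on an intraclass correlation "with 5 observations per subject, level of significance: 0.05, power: 0.8, minimum acceptable reliability: 0.6, expected reliability: 0.8, drop out 10" per cent. The stated result is 28. Whether the test is one- or two-sided is not given.
- **Raters.** "In this study, 2 examiners will be involved for assessment of Landry healing index score of surgical wounds".
- **Repeats.** "Total 2 rounds of examination are completed. Pairs of repeated scores are used to assess intra examiner reproducibility".
- **First end point.** "Calibration process will be repeated until full agreement is achieved between 2 examiners".
- **Second end point.** "Assessment session will end when good or excellent reliability is obtained". The same paragraph classes an ICC of 0.75 to 0.9 as good and above 0.90 as excellent.

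**The concern.** In a reliability sample size, the number of scores per subject is the number that enter each ICC. Two examiners give two scores per subject for the inter-examiner estimate in a round. Two rounds give two scores per subject for each examiner's intra-examiner estimate. Even if every score is counted, a subject has only four. The five in the calculation matches nothing in the exercise described, and it lowers the number of subjects required.

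The Landry score is the outcome for Objective 1, and under Clinical Procedures it is scored by a blinded examiner after calibration. Calibration is the support the plan offers for the reliability of that score, so the power claimed for it should be one the exercise has.

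The end of the exercise is also unclear. An ICC of 0.80 ends the assessment session, yet it is not the full agreement required of the calibration process as a whole.

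**Working it through.** **Inputs.** From the Calibration section: null reliability ρ0 = 0.6, expected reliability ρ1 = 0.8, α = 0.05, power 0.8, loss 10%, m = 5 scores per subject. From the exercise as described: m = 2.

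**Formula** (the standard ICC sample size for the method the plan cites), where n is the number of subjects:

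n = 1 + 2(zα + zβ)² m / [(ln C)² (m − 1)], with C = [1 + mρ0/(1 − ρ0)] / [1 + mρ1/(1 − ρ1)].

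Here ρ0/(1 − ρ0) = 1.5 and ρ1/(1 − ρ1) = 4. For two-sided 0.05, (1.960 + 0.842)² = 7.849.

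**Step 1: the plan's figure (m = 5).** C = 8.5/21 = 0.405 and (ln C)² = 0.818. Then n = 1 + 2 × 7.849 × 5 / (0.818 × 4) = 24.99, so 25. With loss, 25/0.9 = 27.8, so 28, an exact match. A one-sided test gives 19.9, so 20, and 20/0.9 rounds up to 23, which does not match. The plan's figure is therefore two-sided with five scores.

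**Step 2: two scores per estimate (m = 2).** C = 4/9 = 0.444 and (ln C)² = 0.658. Then n = 1 + 2 × 7.849 × 2 / 0.658 = 48.7, so 49. With loss, 49/0.9 = 54.4, so 55. An exact F test gives 50 and 56.

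**Step 3: power of the planned size.** Inverting the formula, power = Φ{√[(n − 1)(ln C)²(m − 1)/(2m)] − zα}. For m = 2 and n = 25, √(24 × 0.658/4) = 1.986, and Φ(1.986 − 1.960) = 0.51.

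| Scores per estimate | Test | 25 evaluable | 28 evaluable |
|---|---|---|---|
| 5 (as planned) | two-sided | 80% | 84% |
| 2 (as described) | two-sided | 51% | 56% |
| 2 | one-sided | 63% | 68% |
| 4 (all scores pooled) | two-sided | 76% | 81% |

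The exact F test for two scores, two-sided, gives 50% and 55%.

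**Step 4: precision.** For a one-way ICC with two scores, F = (1 + ICC)/(1 − ICC), so an observed 0.80 gives F = 9. With 25 subjects the degrees of freedom are 24 and 25. The limits are 9/2.242 = 4.01 and 9 × 2.257 = 20.3. Converting back by (F − 1)/(F + 1) gives a 95% interval of 0.60 to 0.91.

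**Step 5: the end points side by side.** The first belongs to the calibration process, which the section defines as the alignment and assessment sessions together. The second belongs to the assessment session and is an ICC of about 0.75 or more. The first is stricter, and the text does not say which one releases the examiners to start scoring.

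**The case against.** **The power is for a test that will not be run.** This stands. The plan obtains an ICC, classifies it and stops at good or excellent; it compares nothing with 0.6. A reader might infer that calibration has only an even chance of succeeding, and that does not follow. If passing means an estimate of at least 0.75 (F ≥ 7) with two scores and 25 subjects, an examiner pair with a true ICC of 0.8 passes with probability P(F > 7/9) = 73%, and a pair at 0.6 with probability P(F > 7/4) = 8.6%, per attempt. The 51% corrects the planning claim and nothing more.

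**All four scores might be used.** The plan specifies pairs only for the intra-examiner estimate, so a pooled analysis is not excluded, and it would bring power to 76–81%. But one pooled ICC would not separate intra- from inter-examiner reliability, which the section sets out to assess. Four scores also give 27.6, so 28, before any loss, but the text states five and includes a 10% loss.

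**The stopping rules may apply in sequence.** This stands in part. One sentence governs the whole process and the other a single session, so calling them a flat contradiction goes too far. They differ, and the text does not order them.

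**The 0.6 minimum does not conflict with the 0.75 threshold.** This stands. The first is the null value in the sample size, and a pass mark of 0.75 on the estimate is stricter and compatible with it.

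**Calibration may be finished.** It was due before the study began, the study period opens on 1 April 2025, and the document is dated 16 October 2025. If so, recruiting more subjects is moot, but correcting the statement and reporting the results are not.

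**Conclusion.** The concern holds as a mismatch between the calculation and the exercise. The 28 rests on five scores per subject, while each reliability estimate described will have two. For the planning comparison of 0.8 with 0.6, power is about 51% with 25 evaluable subjects and 56% with 28, against the stated 80%. This assumes the two-sided 0.05 that reproduces 28; a one-sided test would give 63–68%, still short. The two end points need to be reconciled.

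A reader might go further in two directions that the documents do not support. The source of the five is not stated, and any explanation for it is a guess. Nor does this bear on the main trial: its 58 participants come from separate calculations, and nothing here shows bias between the arms.

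**What to change.** In the Calibration section:

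1. Change the observations per subject from 5 to 2 and state that the test is two-sided.
2. Keep 28 and restate the power as about 51–56%, noting that 80% would need 49 evaluable subjects, or 55 with loss.
3. Add the expected precision: an observed ICC of 0.80 on 25 subjects has a 95% interval of about 0.60 to 0.91.
4. Replace the two end points with one rule, for example that both the inter- and intra-examiner ICCs are at least 0.75.
5. Report the ICC with its 95% confidence interval for every calibration attempt, not only the last.

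The cost is wording and a short table of results, and the stated power becomes less favourable. No extra subjects are needed; enlarging the exercise to 55, nearly the size of the trial, would not be a cheap change. If calibration is already complete, the restated power and a report of all attempts are still possible; the rule that was actually used should then be stated.

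### More than one surgeon appears to operate, but no section plans to record the operator or include it in the analysis; an operator code and one factor would add modest precision and allow a chance imbalance to be checked.

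*Combined protocol and SAP*

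**What the plan says.** On who operates, the Clinical Procedures section says only "All the surgeries will be performed by qualified operators under aseptic techniques". The number of operators, their grades and their shares of the cases are not given. Near its end, the same section says that the length of the first visit "will depend entirely on factors like type and position of impaction, surgeon's experience, tooth morphology and root anatomy", along with patient factors.

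The Research Variables list has age, gender, angulation and duration of surgery. The list under Data collection method opens with "Data collection form will be prepared for each patient, to record" and names ID, age, gender, tooth angulation, duration of surgery, daily pain, analgesic count and the day 7 Landry score. Neither list has an operator item.

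Allocation is described under Sampling method as "using a simple randomization method based on a pre-generated random number list". The Randomization part of the flowchart adds "A container containing 58 papers with one written number on each will be prepared", with 29 numbers per arm, and the drawn number also becomes the subject ID. Data Analysis names repeated measures ANOVA and the independent t-test, with no factor or covariate other than arm.

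**The concern.** The treatment under test is a rinse used after surgery. All three outcomes follow an operation that includes flap reflection, bone removal, sectioning where needed and suturing. If operators differ in how much tissue trauma they cause, some variation in day 7 healing, pain and mouth opening belongs to the operator and not to the mouthwash.

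Two things follow. That variation stays in the error term of each comparison. And in a trial of 58, one arm may by chance receive more cases from one group of operators; with the planned data set, nobody could report whether that happened or allow for it. The plan already takes care over other sources of variation, with a fixed 08:00 pain reading and examiner calibration. Recording the operator would be in keeping with that.

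**Working it through.** **Inputs from the documents.** Two-sided alpha 0.05, d = 0.8, power 0.8, ratio 1 (objectives 1 and 3); f = 0.4, two groups, seven measurements, correlation 0.5 (objective 2); 10% dropout; 58 randomised as 29 and 29.

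**Assumed, because the documents give no figure.** Two operator grades, each doing half of the cases, that differ by g = 0.3, 0.5 or 0.8 SD on an outcome.

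**1. The plan's own sizes.**
- Two-sample t-test at d = 0.8, noncentral t: power is 0.791 at 25 per arm and 0.807 at 26 per arm. This gives 26 per arm, 52 in total, as stated.
- Repeated measures, between-group test, noncentrality N × f² × 7 / (1 + 6 × 0.5): power is 0.799 at N = 30 and 0.825 at N = 32. This gives 32, as stated.
- Dropout: 52 / 0.9 = 57.8, so 58, as stated.

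No stated figure is wrong.

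**2. Chance imbalance from the 29:29 draw.** Let X be the number of one grade's 29 cases that fall in one arm. X is hypergeometric with variance 29 × 0.5 × 0.5 × 29/57 = 3.69, so its SD is 1.92. The between-arm difference in grade share is (2X − 29)/29, with SD 2 × 1.92/29 = 0.132, or 13 percentage points. The probability of a difference of 10 points or more is 0.60. For 20 points or more it is 0.11; the smallest such difference possible here is 7/29, or 24 points. If one grade does about 30% of cases (17 of 58), the SD is 0.121 and these probabilities are 0.57 and 0.08.

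**3. Shift in the estimate.** Shift = difference in share × g.

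| g (SD) | Shift at 13 points | As share of 0.8 SD |
|---|---|---|
| 0.3 | 0.04 | 5% |
| 0.5 | 0.07 | 8% |
| 0.8 | 0.11 | 13% |

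The less likely 24-point imbalance with g = 0.5 gives 0.24 × 0.5 = 0.12 SD, or 15% of 0.8.

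**4. Power with grade as a factor.** With equal shares, grade explains R² = g²/4 of the outcome variance, and the effective effect size is 0.8/√(1 − R²).

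| g (SD) | R² | Effective d | Power, 26 per arm |
|---|---|---|---|
| none | 0 | 0.800 | 0.807 |
| 0.3 | 0.0225 | 0.809 | 0.816 |
| 0.5 | 0.0625 | 0.826 | 0.832 |
| 0.8 | 0.16 | 0.873 | 0.870 |

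With a 30% share the last three powers are 0.815, 0.828 and 0.860.

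These figures assume that grade is balanced between arms. A 13-point imbalance multiplies the adjusted variance by 1/(1 − 0.132²) = 1.018. With that and 49 instead of 50 degrees of freedom, the powers at equal shares become 0.809, 0.825 and 0.864. At g = 0.3 the precision gain therefore almost vanishes, and what remains is the correction for imbalance.

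These powers apply to the t-test comparisons (Landry and mouth opening). Objective 2 needs only 32 patients, so pain has more margin.

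**The case against.** The strongest case against is that randomisation already deals with this. Chance differences in operator mix are part of the error that the test's alpha allows for, and leaving operator out of the model is a common choice in a small single-centre trial. That stands, and it is why the point is minor. It does not remove the value of knowing who operated.

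The plan also limits surgical variation. It fixes the anaesthetic, flap type and suture, requires bone removal, and excludes deep distoangular and soft-tissue-only impactions. It records "e. Duration of surgery" and "b. Angulation of impacted teeth". These are partial stand-ins, but duration mixes operator with tooth and patient factors, and no adjustment for either variable is planned.

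The form list is clearly not complete: it omits mouth opening, which is an outcome, and a figure within it is not shown. Absence from that list alone is therefore weak evidence. The separate Research Variables list, the draw and the analysis paragraph are equally silent.

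A reader might infer more than the documents support:
- *The plan admits that experience affects the outcomes.* It ties experience only to visit duration.
- *Trainees or junior surgeons operate.* No grade is mentioned, and the plurality of operators rests on one plural noun.
- *An imbalance can never be seen or corrected.* If operative notes identify the surgeon, it can be. The gap is that nothing is prespecified.
- *The comparison is biased.* Any operator imbalance arises by chance, not systematically.
- *Adjustment buys a large gain in power.* A rise to about 0.885 needs grade to explain 20% of variance, and so a gap of 2 × √0.20 = 0.89 SD, larger than the treatment effect the trial is sized for.

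**Conclusion.** The point holds as a small, inexpensive improvement. More than one operator is implied, experience is named as varying, and no section plans to record the operator or to use it in the analysis. The planned tests and sample sizes are unaffected.

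With two equal grades 0.3 to 0.8 SD apart, a typical imbalance moves an estimate by about 0.04 to 0.11 SD, against a design effect of 0.8 SD. Power at 26 per arm goes from 0.807 to about 0.82 to 0.87, and to about 0.83 at 0.5 SD, before the small cost of imbalance shown above. The number of grades, their shares and their effect on outcomes are all assumptions. If every operator is of one grade, the adjustment by grade has nothing to act on and only the operator code is worth keeping.

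**What to change.** - Add operator code and operator grade to the data collection form. For patients already treated, complete both from the operative notes.
- Tabulate operator and grade by arm with the baseline characteristics.
- Before unblinding, prespecify operator grade as one factor in the Landry, pain and mouth-opening comparisons, to apply if more than one grade operated.
- Keep the existing 58-number draw. The document is dated 16 October 2025, within a study period of 1 April 2025 to 31 January 2026, so the draw may be partly used. The drawn numbers are also the subject IDs, and separate sets by grade would no longer guarantee 29 per arm.

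The cost is one extra form entry per patient, some retrieval from notes, and one degree of freedom per comparison. Operators must be pooled into grades, since single operators may have too few cases to model. No extra patients are needed.
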